8.10 Storage and analysis of clinical samples

10mls of venous blood will be withdrawn and collected in pre-chilled sterilins tubes containing EDTA and aprotonin. Blood will be centrifuged at 1500g for 20mins at 4°C. Plasma will be siphoned, aliquoted and stored at -20°C or cooler until transport to the central laboratory on dry ice. At the time of analysis plasma samples will be defrosted at room temperature and analysed in a single batch after 400 patients have completed 60-day follow-up and at the end of the trial. Further details are provided in a laboratory manual.

8.11 End of trial

The overall trial will be deemed complete once 750 patients have experienced a first-event. At that time, an end of trial date will be declared and investigators will be asked to contact all patients on or after that date for a final trial evaluation.

Version 5.0 22 July 2021 Page 43 of 82

The 60-day outcome will be assessed after 400 patients have had their 60-day evaluation. It is anticipated that database lock will occur within three months and that these data will be analysed and presented during the course of the main trial.

9. TRIAL TREATMENTS

9.1 Name and description of investigational medicinal product(s)

Patiromer(as patiromer sorbitex calcium) is a non-absorbed cation exchange polymer that binds free potassium excreted into the gastrointestinal lumen thus increasing faecal potassium excretion and decreasing serum potassium concentrations.

Spironolactone and eplerenone

Spironolactone and eplerenone are mineralocorticoid (aldosterone) receptor antagonists (MRA) that block the actions of aldosterone, causing increased sodium excretion and potassium retention. They are both indicated for the treatment of heart failure. Spironolactone is on the World Health Organization's List of Essential Medicines

9.2 Regulatory status of trial medicines

Patiromer: Patiromer (Veltassa®) is currently licensed in the EU and UK for treatment of hyperkalaemia in adults.

Spironolactone and eplerenone: There are no restrictions on the brand(s) of spironolactone or eplerenone that may be used within the trial provided a Marketing Authorisation is held for the product in the UK.

9.3 Product Characteristics

The sponsor will use the Summary of Product Characteristics (SmPC) for Veltassa and will select a reference SmPC for spironolactone and eplerenone for the Reference Safety Information from the following website https://www.medicines.org.uk/emc/. See Section 10 for further information.

9.4 Patiromer supplies and storage

Trial sites will be supplied with Veltassa®8.4g powder for oral suspension free of charge for participants assigned to the intervention arm. Patiromer will be supplied directly to participating pharmacies by the funder (Vifor) free of charge and will not be modified in relation to its Marketing Authorisation.

Supplies will only be released to trial sites by the sponsor once all the appropriate regulatory and governance approvals are in place. All patiromer packs must be stored in a locked, secure area with access limited to the Investigator and authorised site staff. Supplies must be used as directed in the trial protocol and should not be supplied to any persons other than trial participants.

Investigators may prescribe patiromer for participants assigned to the standard care control group if they believe this is in their best interests. Participants should continue to have follow-up assessments as described in the protocol. However, participants assigned to standard care must not receive trial specific supplies of patiromer-IMP. Any costs associated with patiromer treatment in the standard care group will not be reimbursed from the trial budget and must be met by local payers.

Patiromer must be stored at the site pharmacy between 2°C and 8°C. Once dispensed for participant use, packs can be stored at room temperature below 25°C for up to six months. Visits are planned to

Version 5.0 22 July 2021 Page 44 of 82

occur at no more than 3-month intervals. Supplies must not be used beyond the expiry date. Where possible, supplies of patiromer will be utilised in such a way as to minimise unnecessary wastage.

Further information on ordering, receipt, distribution and destruction of trial medicines is provided in the RELIEHF IMP Management and Accountability Manual.

9.5 Spironolactone and eplerenone supplies and storage

Spironolactone and eplerenone for use in the trial will be sourced from routine NHS hospital supplies and supplied to participants by local investigator site pharmacies.

Depending on participant dose and trial phase, site pharmacies may be required to supply spironolactone 25mg, 50mg and 100mg tablets and eplerenone 25mg and 50mg tablets. There is no requirement to 'ring-fence' supplies for use in the RELIEHF trial and there are no restrictions on the brand(s) of spironolactone or eplerenone that may be used within the trial provided a Marketing Authorisation for the product is held in the UK. Where possible, supplies of spironolactone or eplerenone will be utilised in such a way as to minimise unnecessary wastage. Reimbursement will be available from the trial budget where MRA usage is additional to standard care. All supplies should be stored in accordance with the relevant current Summary of Product Characteristics. Further information is provided in the RELIEHF IMP Management and Accountability Manual.

9.6 Preparation and labelling of Investigational Medicinal Products

Veltassa (Patiromer): Sites will be provided with Annex 13 compliant labels by the sponsor for application at the time of dispensing.

Spironolactone & Eplerenone: Sites will be required to label original packs of spironolactone or eplerenone with Annex 13 compliant labels at the time of dispensing. Usual NHS ward supplies may be used in the run-in phase for in-patient participants where it is in line with local arrangements.

Further information is provided in the RELIEHF IMP Management and Accountability Manual.

9.7 Dosage schedules

Patients with a serum potassium >5.0mmol/L will be shown how to prepare and ingest a single 8.4g test dose of patiromer to ensure that they are willing to take patiromer on a regular basis and to assure the investigator that they understand how to prepare the suspension and requirement to take at least 3 hours before or after other medicines (with key exceptions – see Section 9.8).

Dosing of patiromer and MRA during run-in and at randomisation will be as follows:

- Participants with a serum potassium >5.0mmol/L will be randomised to patiromer 8.4g once daily
 or not and then follow the scheme shown below with evaluation of serum potassium on Days 3, 5 and
 7 and periodically thereafter (see schedule of procedures).
- Participants with a serum potassium ≤5.0mmol/L who are not currently receiving an MRA will first be given spironolactone (or eplerenone[#]) 25mg once daily and randomised to patiromer or not, if and when their serum potassium is >5.0mmol/L. If serum potassium does not exceed 5.0mmol/L within 72 hours, the dose of spironolactone may be increased to 50mg/day and after a further 72 hours to 100mg/day. Those intolerant of or unwilling to take spironolactone should be offered eplerenone (maximum dose 50mg/day).
- Participants with a serum potassium <5.0mmol/L who are currently receiving an MRA at a dose
 of <50mg/day will be initiated on spironolactone 50mg once /daily (or eplerenone*) or if currently
 already receiving 50mg/day, spironolactone 100mg/day (the maximum dose of eplerenone is

Version 5.0 22 July 2021 Page 45 of 82

50mg/day). They will be randomised to receive patiromer or not, only once their serum potassium is >5.0mmol/L.

- Immediately after randomisation: Those assigned to standard care should have the dose of MRA reduced unless serum potassium is ≥6.0mmol/L, in which case MRA should be temporarily suspended altogether until serum potassium is <5.0mmol/L. Patients with a serum potassium >5.0mmol/L who are not taking any dose of MRA may need the dose of other agents that increase potassium reduced. Those assigned to patiromer should continue to receive the dose of MRA administered at the time of randomisation unless serum potassium is ≥6.0mmol/L, in which case MRA should be temporarily suspended and patiromer continued until serum potassium is <6.0mmol/L. If serum potassium is ≥6.0mmol/L, also seek medical advice and treat according to guidelines. If intravenous treatment or a potassium-binding agent for the treatment of severe hyperkalaemia is required in the investigators opinion, the participant can be randomised only after these treatments have been stopped.
- Maintenance Phase: doses should follow the scheme shown in the tables below.
- Participants who do not develop a serum potassium >5.0mmol/L despite 100mg/day of spironolactone or 50mg/day of eplerenone within 35 days are not eligible for the randomised trial and will return to standard care. The clinician responsible for care should select the most appropriate dose of MRA for the participant. Under these circumstances, this will usually be 50mg/day of spironolactone or eplerenone. Participants will continue to be followed in the registry and may be reconsidered for the trial at any time should they become eligible.

If eGFR falls below 30mls/min/1.73m²or systolic blood pressure below 90mmHg prior to randomisation, the participant is not eligible for randomisation until these exclusion criteria have resolved. Under these circumstances, clinicians responsible for care should decide whether to continue the MRA and at what dose. Those excluded will continue to be followed in the registry and may be reconsidered for the trial at any time should they become eligible.

The following maximum doses of MRA are permitted for participants in the intervention arm after randomisation:

• **Spironolactone:** 200mg once daily. All doses must be taken orally.

• **Eplerenone:** 50mg once daily. All doses must be taken orally.

only those intolerant of, or unwilling to take, spironolactone should be offered eplerenone.

Version 5.0 22 July 2021 Page 46 of 82

	Titration of Patiromer and MRA for Patients Assigned to Patiromer							
Serum Potassium #	Patiromer ##	MRA ###	Potassium Supplements	Other Potassium Sparing Diuretics				
<3.5mmol/L	Withhold Patiromer for 48 hrs	Increase MRA Dose unless already on highest dose tolerated	Consider	Consider				
3.5-4.0mmol/L	Maintain Patiromer Dose (unless already on highest dose of MRA, in which case reduce dose of patiromer)	Increase MRA Dose unless already on highest dose tolerated	Withhold	Withhold				
4.1-4.9mmol/L	Maintain Patiromer Dose	Increase MRA Dose unless already on highest dose	Withhold	Withhold				
5.0-5.9mmol/L	Increase Patiromer Dose unless already on highest dose	Maintain MRA Dose unless already on highest dose of patiromer, in which case reduce dose of MRA	Withhold	Withhold				
≥6.0mmol/LII	Increase Patiromer Dose unless already on highest dose	Withhold MRA until serum potassium is <6.0mmol/L then re-start at lower dose. Seek medical advice and treat	Withhold	Withhold				
		according to guidelines I						

Titration of MRA for Patients Assigned to Control						
Serum	MRA ∞	Potassium	Other Potassium			
Potassium #		Supplements	Sparing Diuretics			
<3.5mmol/L	Increase MRA Dose unless already on 50mg/day	Consider	Consider			
3.5-4.0mmol/L	Increase MRA Dose unless already on 50mg/day	Consider	Consider			
4.1-4.9mmol/L	Maintain MRA Dose	Withhold	Withhold			
5.0-5.9mmol/L	Reduce MRA Dose	Withhold	Withhold			
≥6.0mmol/LII	Withhold MRA until serum potassium is <5.0mmol/L then re-start at lower dose	Withhold	Withhold			
	Seek medical advice and treat according to guidelines					

most recent serum potassium – usually measured on the same or previous day. If doses of patiromer or MRA are changed, blood pressure and serum electrolytes and creatinine should be re-checked both after 7-12 days and after 30-45 days. If the patient becomes acutely unwell for any reason, blood pressure, serum electrolytes and creatinine should be re-checked. Serum potassium should also be checked within 48 hours of stopping patiromer.

initial dose is 8.4g/day and may be increased in steps to 16.8g/day or 25.2g/day guided by serum potassium, investigator judgement and patient-acceptance of higher doses. The maximum possible dose is 25.2g/day.

the maximum dose of spironolactone is 200mg/day and of eplerenone 50mg/day and will be guided by serum potassium, symptoms of hypotension, renal dysfunction and patient-acceptance of higher doses. Only those intolerant of or unwilling to take spironolactone should be offered eplerenone.

∞the maximum dose of spironolactone is 200mg/day and of eplerenone 50mg/day and will be guided by serum potassium, symptoms of hypotension, renal dysfunction and patient-acceptance of higher doses. Only those intolerant of or unwilling to take spironolactone should be offered eplerenone.

Management of hyperkalaemia with a serum potassium ≥6.0mmol/L will also follow the Renal Association guidelines of 2020 (https://renal.org/sites/renal.org/files/RENAL%20ASSOCIATION%20HYPERKALAEMIA%20GUIDELINE%202020.pdf). Participants should be recalled urgently to have serum potassium rechecked, clinical review and an electrocardiogram. Referral to an accident & emergency department may be considered. Patiromer https://enal.org/sites/renal.org/files/RENAL%20ASSOCIATION%20HYPERKALAEMIA%20GUIDELINE%2020.pdf). Referral to an accident & emergency department may be considered. Patiromer https://enal.org/sites/renal.org/files/RENAL%20ASSOCIATION%20HYPERKALAEMIA%20GUIDELINE%2020.pdf). Referral to an accident & emergency department may be considered. Patiromer <a href="https://enal.org/sites/rena

Version 5.0 22 July 2021 Page 47 of 82

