The randomised trial will investigate whether patiromer allows patients with worsening heart failure to be titrated to higher doses of MRA (predominantly spironolactone). Participants who are not assigned to patiromer should have titration to guideline-recommended doses of MRA attempted, although many are anticipated not to achieve this. Patients assigned to patiromer may be titrated to 200mg/day of spironolactone (highest licensed dose 400mg/day) or the highest licensed dose of eplerenone (50mg/day). (Eplerenone 50mg/day has similar MRA potency to about 35mg/day of spironolactone; accordingly, spironolactone is the preferred MRA. We expect that the median dose of spironolactone (or eplerenone) in the control group will be 25mg/day and that up to 25% will not tolerate any dose of MRA due to hyperkalaemia or other reasons.) We expect that the median dose of spironolactone in the patiromer-facilitated arm will be about 100mg/day because hypotension and renal dysfunction will prevent many patients from being titrated to 200mg/day and that almost all randomised patients will tolerate some dose of MRA.

The trial is **open-label**, which reduces complexity for participants (those assigned to the control group are not required to take a placebo), increases participant-safety (participants taking patiromer know that if they stop taking either patiromer or MRA this may cause problems), helps investigators and other health professionals manage clinical problems and reduces the logistic complexity of pharmacy trial-supply.

There are two phases to the randomised trial: during the first 60 days, the main aim is to control congestion, thereby improving well-being and reducing the need for hospital care; the long-term aim is to reduce morbidity and mortality. Good control of congestion might reduce the risk of death not only from heart failure but also from arrhythmias (including atrial fibrillation and therefore stroke), bronchopneumonia and end-stage renal disease but is unlikely to alter mortality due to cancer within the time-frame of this trial and consequently cancer deaths will not comprise part of the primary endpoint, although they will be recorded. Potentially spironolactone could have a favourable effect on some cancers (e.g. prostate cancer (19)). Evidence for a detrimental effect on sex-hormone sensitive cancers is lacking (20, 21).

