For patients who do not already have a serum potassium >5.0mmol/L, the initial dose of spironolactone will be 25mg/day for those who are spironolactone naïve and 50mg/day for those already receiving spironolactone or eplerenone at doses <50mg/day. Spironolactone may be increased to 100mg/day if serum potassium remains <5.0mmol/L despite 50mg/day of spironolactone or eplerenone. Only if serum potassium rises to >5.0mmol/L is the patient eligible for randomisation. If eGFR falls below 30ml/min/1.73m² or systolic blood pressure <90mmHg (and this cannot be corrected by altering the dose of other medications), then the patient is not eligible for the randomised trial and will return to standard care. The clinicians caring for the patient should then decide on the most appropriate dose of MRA.

Participants who have or develop a serum potassium >5.0mmol/L can be randomised directly into the trial provided they do not require intravenous treatment or a potassium binding agent for the treatment of severe hyperkalaemia in the investigator's opinion. Severe hyperkalaemia should be managed according to the UK Renal Association guidelines of 2020

(https://renal.org/sites/renal.org/files/RENAL%20ASSOCIATION%20HYPERKALAEMIA%20GUIDELINE%2020 20.pdf). Participants may be reconsidered for the trial once such interventions are no longer considered necessary. For patients assigned to patiromer, the dose of MRA should not be increased until serum potassium drops below 5.0mmol/L (see titration schedule). The dose of patiromer may be increased to achieve a serum potassium in the target range. For patients assigned to the standard care control group, the dose of MRA should be reduced to allow serum potassium to fall into the target range.

MRA (spironolactone or eplerenone) may cause hyperkalaemia, hypotension or renal dysfunction. Hyperkalaemia can be corrected by patiromer, which forms part of the rationale for this trial. If hypotension is symptomatic or renal function deteriorates, this can often be managed by adjusting doses of concomitant medications, including conventional diuretics and non-steroidal anti-inflammatory drugs or, failing that, the dose of MRA may be reduced.

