 Participants may be reconsidered for the trial once such interventions are no longer considered necessary.
 - Patients with a serum potassium ≤5.0mmol/L should be initiated on spironolactone or have the
 dose increased up to 100mg/day and randomised only if serum potassium exceeds 5.0mmol/L.
 Those intolerant of or unwilling to take spironolactone should be offered eplerenone titrated to
 a maximum dose of 50mg/day.
 - A run-in period of up to 35 days is permitted (the run-in period will usually occur during hospitalisation or a course of day-care or intense management).
- 2. After ingestion of a test-dose of patiromer,
 - a) the patient is willing to continue in the trial
 - b) the investigator considers the patient can follow instructions on preparing patiromer

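### The footnote to the control-arm MRA titration table gives a spironolactone maximum of 200 mg/day, although the table's own rows stop increases at 50 mg/day

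*Protocol*

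**What the plan says.** Section 9.7 of the protocol has one titration table per arm, each driven by the most recent serum potassium. In the control table, only the two lowest potassium rows (below 3.5, and 3.5 to 4.0 mmol/L) permit an increase, and both carry the same instruction: "Increase MRA Dose unless already on 50mg/day". The heading of that MRA column bears the mark ∞, and the note under that mark says "the maximum dose of spironolactone is 200mg/day and of eplerenone 50mg/day". The note directly above it, which belongs to the MRA column of the patiromer table, has the same wording.

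Other places bear on which arm the 200 mg/day figure belongs to:

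- The body of section 9.7 introduces its own list of maxima with "The following maximum doses of MRA are permitted for participants in the intervention arm after randomisation", and that list gives spironolactone 200 mg and eplerenone 50 mg once daily.
- Section 2 says "Patients assigned to patiromer may be titrated to 200mg/day of spironolactone (highest licensed dose 400mg/day", and of the control arm "We expect that the median dose of spironolactone (or eplerenone) in the control group will be 25mg/day".
- The Trial Summary, under formulation and dose, gives spironolactone up to 200 mg/day according to potassium and names no arm.

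The dose at which a control enters the table is set by three further statements. In section 7.1, a patient with potassium at or below 5.0 mmol/L may start spironolactone or have the "dose increased up to 100mg/day and randomised only if serum potassium exceeds 5.0mmol/L". After randomisation, section 9.7 says "Those assigned to standard care should have the dose of MRA reduced unless serum potassium is ≥6.0mmol/L", in which case MRA is suspended. Section 3 says that for controls "the dose of MRA should be reduced to allow serum potassium to fall into the target range". The last two give no amount in milligrams.

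**The concern.** A site pharmacist or prescriber looking up a control patient would find two different limits in one table: 50 mg/day in the cells and 200 mg/day in the note attached to the column. Controls are enrolled because their potassium exceeded 5.0 mmol/L, and they are not assigned a binder. An inflated maximum in the working titration scheme is therefore a safety matter as well as an editorial one. It also bears on the comparison, which depends on the patiromer arm reaching MRA doses that the control arm does not. If controls could be taken to the same 200 mg/day, the protocol would no longer define the dose contrast it sets out to test.

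**Working it through.** The protocol makes no calculation here, so there is no figure to reproduce. The check sets the statements side by side.

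**Step 1. Does the footnote belong to the control table?** Yes. The ∞ mark is on the MRA column of the control table and the footnote carries the same mark. The patiromer table uses a different mark with its own note.

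**Step 2. How far apart are the two limits?**

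| Drug | Footnote maximum | Dose at which the table stops increases | Ratio |
|---|---|---|---|
| Spironolactone | 200 mg/day | 50 mg/day | 200/50 = 4 |
| Eplerenone | 50 mg/day | 50 mg/day | 50/50 = 1 |

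The conflict is confined to spironolactone, which the protocol expects to be the main MRA.

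**Step 3. Which figure fits the rest of the protocol?** Section 9.7 (body text) and section 2 both attach 200 mg/day to the patiromer arm. The expected control median is 25 mg/day. The Trial Summary is neutral because it names no arm. Neither body passage states 50 mg/day as the limit for randomised controls; that figure rests on the two table rows. The identical wording of the two notes makes copying from the patiromer note the likeliest explanation, though this is an inference.

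**Step 4. What could the footnote lead to in practice?** The control table by potassium:

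| Serum potassium (mmol/L) | Control-arm MRA |
|---|---|
| below 3.5 | increase, stopping at 50 mg/day |
| 3.5 to 4.0 | increase, stopping at 50 mg/day |
| 4.1 to 4.9 | hold |
| 5.0 to 5.9 | reduce |
| 6.0 or more | withhold until below 5.0, then restart lower |

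Even a prescriber who followed the footnote instead of the cells could raise the dose only at 4.0 mmol/L or below. Section 9.7 also asks for blood pressure, electrolytes and creatinine to be rechecked 7-12 and 30-45 days after a dose change. Section 9.9 reduces or stops MRA for symptomatic hypotension or a persistent eGFR below 30.

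**Step 5. Is the wording of the increase rows sufficient?** Not quite. The stop is written for a patient on exactly 50 mg/day. Run-in can reach 100 mg/day and the cut at randomisation has no stated size. From 100 mg/day, a cut of r leaves 100 − r, which exceeds 50 only if r < 50 mg. As an assumed example, a cut of 25 mg leaves 75 mg/day. If that patient's potassium later fell to 4.0 or below, the row read literally would not stop an increase, and the only printed maximum would be the footnote's 200 mg/day. Extending the stop to 50 mg/day or more closes this.

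The two analogues in the protocol do not produce this case. One step down the run-in ladder in section 9.7 (25, 50, 100 mg/day) takes 100 to 50. The Appendix 3 rule for patients who stop patiromer gives the higher of 100/2 and 25, which is 50 mg/day. Neither is stated as a control-arm rule.

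**The case against.** The best defence is that the footnote is a product-level ceiling, as in the Trial Summary, while the table cells set the stricter arm-specific rule. Section 9.7 directs that maintenance dosing follow the tables, and no row increases a control already at 50 mg/day. The note itself also makes dosing subject to potassium, hypotension and renal function. This shows that a careful reader would probably reach 50 mg/day, and it is why the matter is minor. It does not make the footnote right: the note is attached to the control column, is phrased as that column's maximum, and does not say that a lower limit applies.

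Three stronger readings are tempting and are not supported.

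- *That hyperkalaemic controls could be titrated towards 200 mg/day.* The table permits no increase above 4.0 mmol/L and requires reduction from 5.0.
- *That the protocol wrongly omits a compulsory step-down to 50 mg/day for controls randomised above that dose.* Reduction in controls is deliberately guided by potassium, in section 3 and in the table, and 50 mg/day is written as a stop on increases. A control held at a higher dose with potassium of 4.1 to 4.9 is within the scheme. A stated step-down would be a useful clarification, but its absence is not an error.
- *That the body text of section 9.7 fixes 50 mg/day for controls.* It shows only that its own list of maxima is for the intervention arm.

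**Conclusion.** The ∞ footnote is wrong as written: its spironolactone maximum is four times the dose at which its own table stops increases. The severity is minor. Increases are confined to potassium of 4.0 mmol/L or below, with holding, reduction and withholding above that, and the eplerenone figures agree.

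No reported result is affected. SAP sections 1.6.1 and 1.6.3 record early closure with 4 participants randomised and only summaries or listings. A reader might infer that some control received more than 50 mg/day because of the footnote; the documents contain nothing that shows this.

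The conclusion rests on the table cells, not the footnote, expressing the intended control limit. The patiromer-arm wording in sections 2 and 9.7 supports this but does not prove it. The flow-chart figures are not available in the text reviewed, so a control-arm limit printed there cannot be excluded; it would not remove the conflict within the table.

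**What to change.** Two changes in section 9.7:

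1. Reword the ∞ footnote to say that in the control arm MRA (spironolactone or eplerenone) is not increased above 50 mg/day, keeping the existing qualifications on potassium, hypotension, renal function and patient acceptance.
2. In both increase rows of the control table, extend the exception from patients on 50 mg/day to patients on 50 mg/day or more.

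Optionally, state how far MRA is reduced when a control is randomised on more than 50 mg/day.

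The two required changes amount to one footnote and two table cells, with no effect on sample size, endpoints or analysis. The downside is slightly less freedom to raise the dose in a control who tolerates more. As the trial has closed, the correction serves the protocol of record and any later use of this titration scheme.
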